### Sound Retention Efforts

Using the retention efforts described above and in the Recruitment and Retention attachment, we are confident that we will retain at least 80% of our study sample at the follow-up assessments as we have done previously.

### Data Management

Data will be electronically collected, managed, and secured using REDCap™ by study staff trained on REDCap data entry, management, and security. Quality assurance measures, including built-in skip patterns, validation ranges, and logic checks, minimize data collection and data capturing errors. Quality control measure, including internal monitoring systems and daily and weekly reporting, are run to ensure expedient error correction and to optimize data integrity.

### Study Outcomes

The study outcomes are described in Table 4. The primary outcome of the study is viral suppression which will be operationalized as viral load  $\leq 50$  at 3 months. Viral load is the biologic correlate of the ART adherence behavior; yet, to achieve biologic change, there must be change in the adherence behavior. As suggested through the "Undetectable equals Untransmittable," or "U=U," public health campaign, PLWH who take ART as prescribed and achieve and maintain viral suppression have effectively no risk of sexually transmitting the virus to a serodiscordant partner. Our secondary and related outcomes include ART adherence measured in two ways: 1) a single-item self-report measure, an empirically validated instrument, and 2) electronic pill bottle data, collected via the CleverCap bottle. The electronic

pill bottle data provide a less subjective measure as compared to self-report. We will also measure missed healthcare visits using electronic medical record (EMR) data.

Limitations and Considerations of the Study Outcome. We recognize that all the approaches for measuring viral suppression and ART adherence are limited. First, viral suppression does not directly measure a behavioral outcome but, rather, the biologic effects of the behavior. Second, the self-report measure is biased

**Table 4. Measures and Schedule of Events**

	Screening	Baseline	3 mos
Sociodemographic:(e.g., age, race/ethnicity, education, housing)		X	
Primary Outcome Measures			
Viral Load through dried blood spot kit	X		X
Secondary Outcome Measures			
ART adherence (SRSI)  and the CleverCap (intervention group only)	X		X
Additional Outcome Measures			
Quality of Life (PROMIS-29) 		X	X
HIV Symptom Index 		X	X
Engagement in HIV Care 		X	X
Mediators			
The HIV Medication Taking Self-Efficacy Scale		X	X
Motivation and outcome expectancies of ART adherence are assessed as three separate dimensions: attitudes, norms, and behavioral intentions to adhere to ART medication 		X	X
Self-regulation skills, which include self-monitoring, goal-setting, and enlistment of self-incentives/plans 		X	X
HIV-regulated Stigma 		X	X
Moderators			
Alcohol, Smoking & Substance Involvement Screening Test (ASSIST) 		X	X
Depression and Anxiety (Beck Symptom Inventory) 		X	X

and has ceiling effects. Finally, the electronic pill box is limited to data collected from the intervention group. While this is a limitation, providing the electronic pillbox to the standard of care (control group) is likely to bias our intervention effects since this pillbox will, in fact, have intervention effects as we have found from our preliminary findings from our WiseApp trial. We closely considered each of these limitations and have, therefore, decided that this three-pronged (i.e., viral load, self-report, and electronic pillbox) approach which will provide the most rigorous approach to measuring our primary and secondary outcomes of viral suppression and ART adherence.

## **Mediators**

Several mediators are hypothesized to explain the mechanisms through which the intervention is anticipated to improve viral suppression. Hypothesized mediators include: self-efficacy, motivation expectancies, self-regulation skills, and HIV-related stigma. The HIV Medication Taking Self-Efficacy Scale is also used to measure ART adherence self-efficacy, or the confidence to take medications in various situations. Motivation and outcome expectancies of ART adherence are assessed as three separate dimensions: attitudes, norms, and behavioral intentions to adhere to ART medication. Self-regulation skills, which include self-monitoring, goal-setting, and enlistment of self-incentives/plans, are also assessed. In prior studies of ART adherence, HIV-related stigma and discrimination have been strongly associated with non-adherence; thus, we also measure HIV-related stigma.

## **Moderators**

Several moderators are hypothesized to affect the strength of the intervention to yield improvements in viral suppression and will be explored. Hypothesized moderators include: depression, anxiety and substance use. Depression and anxiety will be measured through the Brief Symptom Inventory, a multi-item scale of mental health in the last seven days that gives a global index and nine primary symptom domains, including depression and anxiety ( $\alpha > 0.80$ ). Problem alcohol and drug use are also assessed with the Alcohol, Smoking & Substance Involvement Screening Test (ASSIST). The ASSIST consists of nine items, covering ten substances (used in the past four months), including: tobacco, alcohol, cannabis, cocaine, stimulants, inhalants, sedatives, hallucinogens, opioids, and other drugs. The ASSIST assesses frequency of use and associated problems for each substance with good to excellent reliability and validity.

## **Other Important Outcomes**

Quality of life will be measured through the PROMIS-29, and an instrument which was validated by [name] for use with PLWH. HIV symptoms and management will be measured with the HIV Symptom Index and Engagement in HIV Care will also recorded at all assessment points.

## **Data Analysis**

The distribution of all variables will be assessed, as will the correlations between all variables and the primary/secondary outcomes. We will assess for patterns of missing data, which are expected to be low as the study utilizes computer-assisted self-interview (CASI) for sensitive data, which reduces participant nonresponse. The primary anticipated reason for missing data is attrition due to loss to follow-up. Based on our preliminary studies, we are accounting for 20% attrition from randomization to the 3-month assessment.

All multivariate analyses will be preceded by standard descriptive bivariate analyses to describe key variables and relationships among them. These analyses will include means, frequency tables, histograms, and examination of distributions. All statistical tests will be two-sided tests with the level of significance at 0.05. The primary hypothesis 1 will be a comparison of viral suppression (primary outcome) between CHAMPS Pilot and standard of care. We will also compare the drop in viral load (measured in logarithmic scale with base 10) between the two groups. Our secondary and related outcome is ART adherence measured in two ways: 1) a single-item self-report measure, an empirically validated instrument (SRSI) and 2) electronic pill bottle data which we will be collecting in the intervention group since all participants will receive a CleverCap bottle for their medications. All the analyses will be based on initial assignment to groups, using the intention-to-treat principle.

The primary hypothesis 1 ( $H_1$ ) will be tested using a generalized linear mixed model (GLMM) with logit-link function for binary outcomes (i.e., viral suppression) or a linear mixed model (LMM) for continuous outcomes (i.e., viral load measured in logarithmic scale) to account for the non-independence of repeated measurements within individuals. The models will include a random intercept and fixed effects for intervention group, time, and interaction term of group and time which is for testing efficacy of the intervention. The model may include

stratification variables, age, and sex as covariates. A site by group interaction will be also examined and included in each model (above) if significant at the .05 level. All analyses will be tested for goodness-of-fit using the Wald-type test, which shows satisfactory performance for models with fewer (<5) covariates. A similar GLMM will be used to test sustainability of the intervention at month 3. For this analysis, we will conduct a non-inferiority test to compare viral suppression rate between month 3 and baseline. For primary hypothesis 2 ( $H_2$ ), testing for intervention effect on ART adherence measured by SRSI (secondary outcome), we will use a similar LMM as mentioned above. For electronic pill bottle data in the intervention group, we will also examine the trend of electronic pill bottom data over time with a GLMM which will include a first-order autoregressive (AR1) covariance structure, as described by Hedeker and Gibbons. We will also aggregate the electronic pill bottle data at different time points (0 and 3 months) and examine the association between the electronic pill bottle data and ART adherence data measured by SRSI using Spearman nonparametric correlation. Similar GLMMs or LMMs will be used for secondary outcomes, with GLMMs for binary outcomes and LMMs for continuous outcomes.

Aim 2. Conduct follow-up interviews to assess the barriers and facilitators to the recruitment, enrollment and retention procedures and to understand the acceptability of the intervention.

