### Design Overview

A pilot study will be conducted with 40 PLWH over 3 months. Participants will be randomly assigned to CHAMPS Pilot (intervention) or a standard-of-care control arm.

**Intervention Arm:** The CHAMPS Pilot intervention, outlined in Table 1, is a 3-month intervention guided by BA2C. The CHW will be demographically-matched to our study participant.

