## Eligibility Criteria for Participants

***Inclusion criteria:*** 1) Able to speak, read, and write in English or Spanish, 2) Aged  $\geq 18$  years; 3) Willing to provide a valid form of identification for verification; 4) Willing to participate in any assigned arm of the intervention; 5) Having been diagnosed with HIV  $\geq 6$  months ago; 6) Have an HIV-1 RNA level  $>50$  copies/mL, or at least one “no-show” visit in the past 12 months, or report either not virally suppressed in the past 12 months or virally unsuppressed in the past 12 months; 7) Own a smartphone; 8) Ability and willingness to provide informed consent for study participation and consent for access to medical records; and 9) Live in the United States.

***Participants are not eligible if they meet any exclusion criteria:*** 1) Reside in a nursing home, prison, and/or receiving in-patient psychiatric care at time of enrollment; 2) Terminal illness with life expectancy  $<3$  months; and 3) Planning to move out of the country in the next 3 months.

***Inclusion consideration:*** We carefully considered including newly diagnosed patients (diagnosed  $<6$  months) and have chosen to not include this subset of PLWH because: 1) Our piloted interventions did not include newly-diagnosed persons; 2) Newly-diagnosed individuals are treatment naïve and their adherence behaviors are unknown and may change frequently as they begin their ART regimen; and 3) The advent of rapid-start ART for newly-diagnosed individuals is currently under trial, providing an ART-initiation intervention for these individuals that could compromise our study results.

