### Randomization

Using the randomization approach described below, there will be random or minimally biased assignment of subjects to study arms. Randomization will be achieved through a blocked design utilizing permuted blocks of random sizes. The design ensures equal representation of treatment assignment across groups and protects the study team and investigators from easily anticipating treatment allocation. Randomization to CHAMPS Pilot or standard of care is 1:1. Participants will be randomized using computer-generated random numbers at baseline. The randomization database will be stored on a password protected computer at Columbia University and will only be accessible to PI [name]. Following completion of the informed consent and baseline assessment, participants will be randomly assigned to one of two trial arms in REDCap.

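### The between-arm test of the drop in log10 viral load is an unadjusted change-score comparison. It is valid, but adjusting month 3 for the entry value would make it more precise, by an amount the documents do not let one fix.

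*Combined protocol and SAP*

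**What the plan says.** Under Data Analysis (Aim 1), hypothesis 1 has a binary analysis (suppression, the primary outcome) and a continuous one. On the continuous one the plan says: "We will also compare the drop in viral load (measured in logarithmic scale with base 10) between the two groups". The linear mixed model has a random intercept and "fixed effects for intervention group, time, and interaction term of group and time which is for testing efficacy of the intervention". Covariates are optional, and those named are "stratification variables, age, and sex as covariates". The Randomization section describes permuted blocks of random size and names no stratification factor, so entry viral load does not come in that way.

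Table 4 lists viral load at screening and at 3 months only. Under Eligibility Screening, anyone without a result from the previous 8 weeks must give a screening dried blood spot. Each participant should therefore have an entry value, either from records or from a study sample.

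The Sample Size and Power Calculation section sets no power target. It says the sample is meant to give an effect size for planning later trials and to show feasibility.

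**The concern.** A change score fixes the coefficient of the entry value at 1. There are two reasons to expect a true slope below 1 here. A participant who becomes suppressed ends at the same floor whatever the entry value, so most of that person's drop is simply the entry value. And the main eligibility list admits people who may already be at or below 50 copies/mL and so cannot drop: a missed visit alone qualifies, as does a person who can "report either not virally suppressed in the past 12 months".

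When the slope is below 1, a chance difference between arms in entry viral load feeds into the estimated effect: the arm with the higher entry load tends to show the larger drop. Randomisation removes this on average but not in a given trial of 40. What is at stake is the precision of an effect estimate that the plan wants for designing later trials.

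**Working it through.** **1. What the planned term estimates.** With two times, complete data and a free group main effect, the group-by-time coefficient is the difference between arms in mean change. Fitting the planned model by REML to two simulated complete data sets gave the same estimate and SE as the plain change-score difference: −0.973 (SE 0.361) by both methods, and −0.598 (SE 0.264) by both. The random intercept handles within-person correlation; it does not adjust the arms to a common entry value.

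**2. Inputs from the plan.** Size: "A pilot study will be conducted with 40 PLWH over 3 months". Allocation: "Randomization to CHAMPS Pilot or standard of care is 1:1". Attrition: "we are accounting for 20% attrition from randomization to the 3-month assessment". Tests: "All statistical tests will be two-sided tests with the level of significance at 0.05". Completers: 40 × 0.8 = 32, or 16 per arm. The plan gives no power figure to reproduce.

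**3. Assumptions.** Difference 0.2 to 1.0 SD, correlation ρ between entry and month 3 of 0.3 to 0.7, and (first) equal SDs at both times.

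**4. Variance per participant, in units of SD².** Change score: 2(1−ρ). Month 3 adjusted for entry: 1−ρ². Ratio: (1+ρ)/2, that is 0.65, 0.75 and 0.85 at ρ = 0.3, 0.5 and 0.7.

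**5. Power at 16 per arm** (noncentral t; 30 df for change, 29 for adjusted). Example at 0.8 SD and ρ = 0.5: the change-score SE is √(2×1/16) = 0.354, so the noncentrality is 0.8/0.354 = 2.26 and power 59.1%. The adjusted SE is √(2×0.75/16) = 0.306, noncentrality 2.61, power 71.4%. The same steps give, change → adjusted:

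| Difference | ρ = 0.3 | ρ = 0.5 | ρ = 0.7 |
|---|---|---|---|
| 0.2 SD | 7.5 → 8.8% | 8.5 → 9.7% | 10.9 → 11.9% |
| 0.3 SD | 10.7 → 13.8% | 13.0 → 15.8% | 18.5 → 21.0% |
| 0.5 SD | 21.2 → 30.0% | 27.8 → 35.2% | 42.4 → 48.2% |
| 0.8 SD | 45.7 → 63.0% | 59.1 → 71.4% | 80.7 → 86.5% |
| 1.0 SD | 63.8 → 81.7% | 78.1 → 88.4% | 94.2 → 96.9% |

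The gains run from about 1 to about 18 points.

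**6. Against the mixed model with entry-only participants kept.** If all 20 per arm contribute an entry value, the planned variance becomes (1−ρ²) + (1−ρ)²×16/20. At ρ = 0.3 that is 0.91 + 0.392 = 1.302, against 1.4 for completers only. At 0.8 SD the gains shrink to about 15, 10 and 5 points for ρ = 0.3, 0.5 and 0.7. Over the whole grid they are about 1 to 15.

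**7. Unequal SDs.** With entry SD σ₀, month-3 SD σ₁ and slope β = ρσ₁/σ₀, the change-score variance exceeds the adjusted variance by (σ₀ − ρσ₁)² = σ₀²(1−β)². This is never negative, and it is zero when β = 1. For a difference of 0.8 month-3 SDs (normal approximation), an entry SD 0.75 times the month-3 SD gives gains of 0.1 to 8.6 points, and one 1.25 times as large gives 17.8 to 27.0.

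**8. Simulation with a floor at 50 copies/mL (log10 about 1.7).** A fraction s is at 1.7 on entry and the rest are N(4, SD 0.9). Of those suppressed at entry, 95% stay so. The others reach 1.7 with an arm-specific probability, or else move by N(0, SD 0.5). With 16 per arm and 6,000 runs, power for change → adjusted was:

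| Suppression, control vs intervention | s = 0 | s = 0.2 | s = 0.4 |
|---|---|---|---|
| 30% vs 70% | 50.4 → 54.5% | 34.7 → 42.8% | 23.9 → 32.2% |
| 20% vs 70% | 72.5 → 74.8% | 53.5 → 63.1% | 37.7 → 47.8% |

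Repeat runs moved single gains by about a point; overall they were 2 to 11 points, with type I error near 5% for both methods. A different floor model, which shifts every intervention participant by 1.0 log10 (SD 1.2) and then truncates, gave 18 to 25 points. I do not build on it, because a uniform shift describes suppression poorly, but it shows how far the answer depends on the model.

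**The case against.** The strongest reply is that nothing is broken. The change-score contrast is unbiased under randomisation and keeps its type I error. Feasibility is Aim 1, the primary outcome is binary suppression, the log10 comparison is an addition to it, and no power target depends on it. All of that stands, and it limits the weight of the point.

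The size of the gain can also be challenged. The largest figures need a large effect, a low correlation and SDs that are at least equal. For differences of 0.2 to 0.3 SD the gain is about 1 to 3 points. If nobody is suppressed at entry, which is how the Characteristics of the Population section describes the trial, the floor simulation gives only 2 to 4 points. The larger floor gains need 20% to 40% already suppressed, a share the documents do not state. This stands too.

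A reader might go further and infer that the log10 drop is the more informative of the two hypothesis 1 analyses, so that its precision decides what the pilot can show. The documents do not say so and the simulation does not bear it out. A plain chi-square test of month-3 suppression beat the change score in all six settings (for example 63% against 50%) and beat the adjusted analysis in four, although Fisher's exact test fell below the adjusted analysis in all six.

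What the objections do not touch is the direction: for given SDs and correlation the adjusted variance is never larger, apart from one degree of freedom. The absence of a power target is no defence either, since estimating an effect size is a stated purpose.

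**Conclusion.** The point holds as a matter of efficiency, at modest weight. For complete data the planned test is an unadjusted change-score comparison, and it leaves unused the adjustment that an already collected entry value allows. The gain is about 1 to 18 points of power at 16 per arm with equal SDs, differences of 0.2 to 1.0 SD and ρ of 0.3 to 0.7. It is slightly less against a mixed model that keeps entry-only participants, about 2 to 11 points in the floor simulation of suppressed versus unsuppressed outcomes, and near zero if the slope on entry is close to 1. Every one of these figures rests on assumed SDs, correlation and effect.

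A reader might infer that the planned test is biased or invalid, or that the primary outcome is affected. Neither follows: the test is sound, and the point concerns only the continuous log10 comparison.

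**What to change.** For log10 viral load, pre-specify as the efficacy estimate the month-3 difference between arms adjusted for entry log10 viral load. The preferable form is the same linear mixed model with the group main effect removed, so that both arms share one entry mean, and an unstructured 2×2 covariance. It keeps every randomised participant with an entry value, in line with the plan's intention-to-treat statement. ANCOVA on completers is the simple alternative. Entry viral load should not merely be added to the covariate list of the present model, where it is already a response. Report the adjusted difference with its 95% CI, and keep the raw mean drop per arm as description.

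The cost is a sentence or two of analysis text, settled before outcome data are seen, and one degree of freedom. There are no new visits, samples or staff. The plan should also acknowledge that entry values may mix record results up to 8 weeks old with screening dried blood spots.

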### Eligibility Screening

Potential participants will either call, text, or email the study team via the advertised phone number or email address. Screening will be conducted over the phone or electronically via REDCap. Each potential participant will be screened for eligibility based on the inclusion/exclusion criteria. Participants who do not have a recent ( $\leq 8$  weeks) available viral load test result will need to complete a study DBS (dried blood spot) collection as part of a screening visit. Participants may also sign a Release of Information (ROI) form to allow study staff to access their electronic medical record (EMR) and determine eligibility based on past viral load data and "no-show" visits. Forms completed electronically will be conducted via video conferencing such as Skype, Zoom, or FaceTime using REDCap to collect the e-ROI and answer participant questions. Through the REDCap platform, participants will be able to securely download a copy of the e-ROI for their records. As part of the REDCap e-consent platform e-ROIs will be automatically archived and securely stored in REDCap. If deemed eligible, staff will work with the potential participant to schedule an enrollment visit at a convenient time for the participant.

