### Procedures

All study visits will occur remotely via Zoom. Staff members will collect digital informed consent prior to enrolling into the study trial (See Protection of Human Subjects). The informed consent form provides details of the study procedures, risks, benefits, site contact information, and the nature of confidentiality and voluntary participation. The consent process also covers information on the study and compensation for time.

Participants in both the intervention and control arms will complete remote visits at the baseline and 3-month follow-up. Following the completion of the baseline study instruments, study participants in the CHAMPS Pilot intervention arm will be mailed a CleverCap™ Lite dispenser and trained on how to use it; they will also be trained by study team members on how to use the different features of the Wise App and receive medication reminders. Upon assignment to the intervention arm, a CHW is assigned to and meets with the participant as soon as possible, generally on the same day but no more than five business days. The CHW will deliver the interventions outline in Table 3 remotely throughout the course of the study. Participants will also be provided the opportunity to complete a follow-up interview at their follow-up visit. Follow-up interviews will be recorded via Zoom and will be semi-structured. Study staff members will take field notes and interview recordings will be transcribed prior to analysis.

Dried Blood Spot (DBS) kits will be used to measure participant viral load. DBS kits will be shipped to participants, allowing them to collect their sample in their home or other secure environment. Instructions will be included with the kit, including information about how to collect the dried blood spot and how to mail the sample back to the research team. Participants will be instructed to call research staff to confirm they have

received the kit, have collected the sample, and have mailed the sample back, as well as if they have any questions.

Participants will be texted appointment reminders for study visits. Hard to reach participants will also be sent scheduling reminders. These reminders will be sent via Qualtrics, REDCap and/or encrypted e-mails from the study's secure CUMC e-mail address.

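### The supporting log10 viral load comparison uses an ordinary linear mixed model with no censoring term, so results reported only as below an assay limit would pull its effect estimate toward zero under the usual substitutes

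*Combined protocol and SAP*

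**What the plan says.** Study Outcomes names a single primary outcome: "The primary outcome of the study is viral suppression which will be operationalized as viral load" of at most 50 at 3 months. It motivates that choice by the "Undetectable equals Untransmittable" campaign.

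The Aim 1 Data Analysis section defines hypothesis 1 as a comparison of viral suppression and then adds: "We will also compare the drop in viral load (measured in logarithmic scale with base 10) between the two groups". The paragraph on testing hypothesis 1 gives a logit mixed model for the binary outcome and, for log10 viral load, "a linear mixed model (LMM) for continuous outcomes (i.e., viral load measured in logarithmic scale". On structure: "The models will include a random intercept and fixed effects for intervention group, time, and interaction term of group and time", with the interaction as the test of efficacy.

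On measurement, Procedures states: "Dried Blood Spot (DBS) kits will be used to measure participant viral load". Table 4 schedules viral load at screening and at 3 months. Under Eligibility Screening, a study blood spot at screening is required only from people without a result from the last 8 weeks: those with no recent "available viral load test result will need to complete a study DBS (dried blood spot) collection as part of a screening visit". A viral load above 50 is one of several routes into the trial. Eligibility Criteria for Participants also accepts a missed "visit in the past 12 months, or report either not virally suppressed in the past 12 months".

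The documents do not give an assay limit, a value for undetectable results, a censored model or a sensitivity analysis for this. The nearest text is a general check of distributions and a Wald-type goodness-of-fit test.

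**The concern.** An ordinary Gaussian model has to be given a number for each result. A result reported only as below a limit is not a number, and a participant who reaches the trial's own definition of success is the most likely to have one. Any constant put in its place collapses a spread of low values to one point, and does so more often in the arm with more suppression. The between-arm difference in log10 drop is then shrunk by an amount that depends on the assay and grows with the proportion censored. Fixing a substitution rule in advance would remove the analyst's discretion but not this bias.

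Censoring can occur at both ends of the drop. Entry through a missed visit or self-report allows baseline values at or below 50. Because the baseline value may come from an existing record, the two visits may also have different limits.

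At stake is the log10 effect size. Sample Size and Power Calculation gives estimation of an effect size for later efficacy trials as one of the two purposes of the sample. An attenuated or arbitrary value carried forward would misinform those trials.

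**Working it through.** **No figure to reproduce.** The plan states no SD, effect size or power for viral load.

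**Inputs from the documents.** 40 participants, 1:1 allocation, 20% attrition: 40 × (1 - 0.20) = 32 completers, 16 per arm. Suppression threshold 50. Group-by-time interaction as the efficacy test.

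**Assumptions, not in the documents.** Normal latent log10 viral load with SD 1.3; control mean at month 3 of 2.0, 2.5 or 3.0; true difference -0.8; assay limit of 20 to 1000 copies/mL.

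**Formula.** With complete data at two visits, the interaction estimate equals the between-arm difference in mean change. Randomisation gives both arms the same expected baseline, so the expected estimate is the difference in month-3 means after substitution. For latent mean m, SD d, log10 limit L and log10 substitute s, let a = (L - m)/d and p = Φ(a). Then

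mean after substitution = p·s + (1 - p)·m + d·φ(a).

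**Worked case: limit 50 (L = 1.699), control mean 2.5, intervention mean 1.7, substitute 50.**
- Control: a = -0.616, p = 0.269, φ = 0.330; mean = 0.269 × 1.699 + 0.731 × 2.5 + 1.3 × 0.330 = 2.71.
- Intervention: a = -0.001, p = 0.500, φ = 0.399; mean = 0.500 × 1.699 + 0.500 × 1.7 + 1.3 × 0.399 = 2.22.
- Difference: about -0.50, against a true -0.80.

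**Effect of the substitute.** Moving from L to another value shifts the estimate by -(difference in proportion censored) × (L - s). Here that difference is 0.500 - 0.269 = 0.231. Using half the limit shifts it by -0.231 × 0.301 = -0.07; using 1 copy shifts it by -0.231 × 1.699 = -0.39, to about -0.89.

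**All three control means, limit 50, by the same formula:**

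| Control mean | Censored, control / intervention | Substitute 50 | Substitute 25 | Substitute 1 |
|---|---|---|---|---|
| 2.0 | 41% / 65% | -0.38 | -0.45 | -0.79 |
| 2.5 | 27% / 50% | -0.50 | -0.57 | -0.89 |
| 3.0 | 16% / 35% | -0.60 | -0.66 | -0.93 |

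Simulation of 600 trials per setting agrees to within about 0.03: -0.37 to -0.59 with 50 substituted and -0.78 to -0.90 with 1 copy. The loss with 50 is 1 - 0.59/0.8 = 26% to 1 - 0.37/0.8 = 54% of the true difference. Across limits of 20 to 1000, substituting the limit gave -0.67 (17% censored) to -0.11 (85% censored).

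**Two-visit check under other assumptions** (4000 simulated trials, 16 per arm, limit 50, SD 1.2, within-person correlation 0.5). With 15% suppressed at baseline and 30% versus 50% at month 3, the latent difference is -0.63. The planned analysis averages -0.39 (substitute 50), -0.45 (25), -0.47 (20) and -0.72 (1 copy), with an empirical standard error of 0.35 to 0.55. With 30% at baseline and 40% versus 70%, the latent difference is -0.94 and the estimates run from -0.42 to -0.93.

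**Censored likelihood.** Fitted to the simulated month-3 values without baseline, it gave a median of -0.76 to -0.78 at a limit of 50 and -0.75 to -0.81 across all limits. The two-visit censored mixed model recommended below was not itself simulated.

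**The case against.** The strongest reply is that the premise is inferred. The documents give no detection limit; 50 is a suppression threshold. A reader might conclude that the target outcome lies at the assay floor, but nothing in the text establishes that. A floor well below 50 would weaken the problem. The extreme of -0.11 needs a limit of 1000, at which the assay could not measure the primary outcome at all, which would be a separate and larger defect. This stands, and it is why the size is given as a range.

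Second, a reader might infer that the result hinges on which substitute the analyst picks. Among ordinary choices it does not. Going from 50 to 20 copies with a 20-point difference in suppression shifts the estimate by 0.20 × 0.398 = 0.08 log10, small against a standard error of about 0.35 to 0.40. The large contrast requires coding undetectable as 1 copy, which the documents nowhere propose. This also stands. But agreement among the usual substitutes is no reassurance, since they are all biased in the same direction.

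Third, it can be said that only a handling rule is missing, and that the distribution and goodness-of-fit checks would expose any trouble. They might expose it, but they do not handle censoring, and the working shows that adding a substitution rule leaves the attenuation in place.

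Fourth, the remedy has limits. At 16 per arm the single-visit censored estimates had an SD of 0.45 to 0.61, with 5th to 95th percentiles of about -1.7 to +0.1 at a limit of 50. At a limit of 1000 and a control mean of 2.0, 23% of trials had an arm fully censored, where no finite estimate exists. This stands and shapes the fix.

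**Conclusion.** The point holds for the log10 viral load comparison. The named model is unsuited to data in which success may be reported only as below a limit, and the usual substitutes do not repair it. At an assumed limit of 50 and a true difference of -0.8, substituting the limit loses roughly a quarter to a half of the effect. Coding undetectable as 1 copy lands near the true value or beyond it, but only because of where that arbitrary code happens to sit. These sizes rest on an assumed limit, SD, true difference and normal latent distribution, none of which is in the documents.

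A reader might infer that the primary result is compromised, because the linear mixed model appears in the paragraph on hypothesis 1. The documents do not support that. Study Outcomes names binary suppression alone as primary, and Data Analysis introduces the drop as an additional comparison. The binary outcome does not depend on any substitute provided the assay resolves 50. The consequence is confined to the supporting analysis and to any log10 effect size taken from it. It is worth correcting because estimating an effect size is a stated purpose of the pilot.

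**What to change.** 1. State the limit of the study blood-spot assay, and record for every viral load which assay produced it (study blood spot or existing record) and that assay's limit.
2. Keep the random intercept and the group, time and group-by-time terms, but fit the log10 viral load model with a left-censored likelihood. A result below the limit, at screening/baseline or at month 3, contributes the probability of lying below the limit of its own assay.
3. Do not enter a substituted baseline value as an ordinary covariate; it can itself be censored or come from another assay. Modelling both visits as outcomes avoids this.
4. Add a rank-based comparison of month-3 values, with everything below the highest limit in use tied at the lowest rank.
5. If most values are censored, or an arm is fully censored, rely on the rank comparison and the binary outcome and do not carry a log10 effect size forward. Define the cut-off for most in advance.

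The cost is SAP wording, standard software and one recorded field per result. Visits, sample size and participant burden do not change. The drawbacks are a distributional assumption below the limit and wide intervals at about 16 per arm. The rank comparison guards against the first, but gives a test and not a log10 effect size.
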